1.4.2 Potential risks

1.4.2.1 Durvalumab

Risks with durvalumab include, but are not limited to, diarrhea/colitis, abdominal pain, pneumonitis/ILD, endocrinopathies (hypo- and hyperthyroidism, type I diabetes mellitus, hypophysitis and adrenal insufficiency, Thyroiditis) hepatitis/increases in transaminases, nephritis/increases in creatinine, pancreatitis/increases in amylase and lipase, rash/pruritus/dermatitis, pemphigoid, myocarditis, myositis/polymyositis, inflammatory events including neuromuscular toxicities (myasthenia gravis), infusion-related reactions, immune thrombocytopenia, hypersensitivity reactions and infections/serious infections.

For information on all identified and potential risks with durvalumab please always refer to the current version of the durvalumab IB.

Clinical Study Protocol
Drug Substance DURVALUMAB/TREMELIMUMAB
Study Number ESR 15-11561-61-DUNE
EudraCT Nº: 2016-002858-20
Edition Number: 5.0 dated on June 09th, 2021

In monotherapy clinical studies AEs (all grades) reported very commonly ($\geq 10\%$ of patients) are cough/productive cough, diarrhoea, abdominal pain, hypothyroidism, rash pruritus, pyrexia, and upper respiratory tract infections

Approximately 9% of patients experienced an AE that resulted in permanent discontinuation of durvalumab and approximately 6% of patients experienced an SAE that was considered to be related to durvalumab by the study investigator.

ImAEs: immune-mediated pneumonitis, hepatitis, colitis, hypothyroidism, hyperthyroidism, adrenal insufficiency, Type 1 diabetes mellitus, hypophysitis/hypopituitarism, nephritis, rash and pemphigoid. Other immune-mediated adverse reactions including myocarditis and myositis/polymyositis. These imAEs should be managed based on dosing and Toxicity Management Guidelines described in appendix 1 of this protocol.

Infusion-related reactions: as with the administration of any Ig, infusion-related reactions may occur and may be severe and should be managed according to Toxicity Management Guidelines and study protocol.

As patients with previous history of bleeding and/or who are taking anticoagulant medications may have a higher risk of subsequent bleeding, the investigator should devote special attention to monitoring of these patients in the context of possible bleeding.

Further information on these risks can be found in the current version of the durvalumab IB.

In monotherapy clinical studies AEs (all grades) reported very commonly ($\geq 10\%$ of patients) are fatigue, cough, decreased appetite, dyspnoea, nausea, constipation, diarrhoea, pyrexia, back pain, anaemia, vomiting, pruritus, arthralgia, headache, asthenia, oedema peripheral and rash.

A total of 178 patients (9.4%) discontinued from study treatment due to an AE. A total of 108 patients (5.7%) had serious AEs (SAEs) that were considered by the investigator as related to durvalumab.

Most treatment-related AEs were manageable by delaying or interrupting the durvalumab dose, symptomatic treatment, and in the case of events suspected to have an immune basis, the use of established treatment guidelines for immune-mediated toxicity (see the Dosing Modification and Toxicity Management Guidelines).

Serious adverse reactions for durvalumab monotherapy considered expected

MedDRA (v21.1) SOC	PT	Number (%) of subjects exposed (N=3006)		
		Suspected SARs n (%) ^a	Occurrence of life-threatening suspected SARs n (%) ^b	Occurrence of fatal suspected SARs n (%) ^b
Respiratory, thoracic, and mediastinal disorders	Pneumonitis	28 (0.9)	0	0
	Interstitial lung disease	7 (0.2)	0	0
Injury, poisoning, and procedural complications	Infusion related reaction	6 (0.2)	0	0
	Pneumonia	7 (0.2)	0	0
Infections and infestations	Pneumocystis jirovecii pneumonia	2 (<0.1)	0	0
	Lung infection	2 (<0.1)	0	0
Gastrointestinal disorders	Colitis	4 (0.1)	0	0
	Diarrhoea	6 (0.2)	0	0
	Abdominal pain	2 (<0.1)	0	0
Endocrine disorders	Adrenal insufficiency	3 (<0.1)	0	0
	Hyperthyroidism	2 (<0.1)	0	0
	Hypopituitarism	2 (<0.1)	0	0
Hepatobiliary disorders	Hypothyroidism	3 (<0.1)	0	0
	Hepatitis	2 (<0.1)	0	0
Investigations	Autoimmune hepatitis	2 (<0.1)	0	0
	AST increased	2 (<0.1)	0	0
	ALT increased	2 (<0.1)	0	0

MedDRA (v19v21.1) SOC	PT	Number (%) of subjects exposed (N=18893006)		
		Suspected SARs n (%) ^a	Occurrence of life-threatening suspected SARs n (%) ^b	Occurrence of fatal suspected SARs n (%) ^b
Renal and urinary disorders	Nephritis	2 (<0.1)	0	0

Pooled dataset from studies CD-ON-MEDI4736-1108 (DCO 16 October 2017), ATLANTIC (DCO 3 June 2016) and, MYSTIC, EAGLE, ARCTIC, CONDOR, HAWK, PACIFIC (DCO 22 March 2018), and D4190C00002.

^a n = number of subjectspatients who have experienced the SAR.

^b All fatal and all life-threatening events for durvalumab monotherapy are considered unexpected for reporting purposes and are excluded from this table.

AST = aspartate aminotransferase; DCO = data cut-off; MedDRA = Medical Dictionary for Regulatory Activities; PT = preferred term; SAR = serious adverse reaction; SOC = system organ class.

The majority of treatment-related AEs were manageable with dose delays, symptomatic treatment, and in the case of events suspected to have an immune basis, the use of established treatment guidelines for immune-mediated toxicity (please see Appendix 1)

A detailed summary of durvalumab monotherapy AE data can be found in the current version of the durvalumab IB.

1.4.2.2 Tremelimumab

Potential risks, based on the mechanism of action of tremelimumab and related molecules (ipilimumab) include potentially immune-mediated gastrointestinal (GI) events including enterocolitis, abdominal pain, dehydration, nausea and vomiting, and decreased appetite (anorexia); dermatitis including urticaria, skin exfoliation, and dry skin; endocrinopathies including hypophysitis, adrenal insufficiency, and hyperthyroidism and hypothyroidism; pancreatitis including

Clinical Study Protocol
Drug Substance DURVALUMAB/TREMELIMUMAB
Study Number ESR 15-11561-61-DUNE
EudraCT Nº: 2016-002858-20
Edition Number: 5.0 dated on June 09th, 2021

autoimmune pancreatitis and lipase and amylase elevation; respiratory tract events including pneumonitis and interstitial lung disease (ILD); nervous system events including encephalitis, peripheral motor and sensory neuropathies, and Guillain-Barré syndrome; cytopenias including thrombocytopenia, anemia, and neutropenia; infusion-related reactions; anaphylaxis; and serious allergic reactions. The profile of AEs and the spectrum of event severity have remained stable across the tremelimumab clinical program and are consistent with the pharmacology of the target. To date, no tumor type or stage appears to be associated with unique AEs (except for vitiligo that appears to be confined to patients with melanoma). Overall, 944 of the 973 patients (97.0%) treated with tremelimumab monotherapy as of the data cutoff date of 1 November 2015 (not including 569 patients who have been treated in the ongoing blinded Phase IIb Study D4880C00003) experienced at least 1 AE. The events resulted in discontinuation of tremelimumab in 10.0% of patients, were serious in 36.5%, were Grade ≥ 3 in severity in 49.8%, were fatal in 67.7%, and were considered to be treatment related in 79.1% of patients. The frequency of any AEs and Grade ≥ 3 AEs was generally similar across the tremelimumab dose groups. However, a higher percentage of patients in the 10 mg/kg every 28 days and 15 mg/kg every 90 days groups compared with the All Doses <10 mg/kg group experienced treatment-related AEs, SAEs, AEs resulting in discontinuation of investigational product (IP), and deaths.

Clinical Study Protocol
 Drug Substance DURVALUMAB/TREMELIMUMAB
 Study Number ESR 15-11561-61-DUNE
 EudraCT Nº: 2016-002858-20
 Edition Number: 5.0 dated on June 09th, 2021

Serious adverse reactions for the tremelimumab monotherapy pool considered expected

MedDRA (v22.0) SOC	PT	Number (%) of subjects exposed Tremelimumab RSI pool (N=1665)		
		Suspected SARs ^a n (%)	Occurrence of life-threatening suspected SARs ^b n (%)	Occurrence of fatal suspected SARs ^b n (%)
Endocrine disorders	Hypophysitis	13 (0.8)	0	0
	Adrenal insufficiency	7 (0.4)	0	0
	Hyperthyroidism	5 (0.3)	0	0
	Hypothyroidism	4 (0.2)	0	0
	Lipase increased	2 (0.1)	0	0
Gastrointestinal disorders	Diarrhoea	183 (11.0)	0	0
	Colitis	68 (4.1)	0	0
	Enterocolitis	4 (0.2)	0	0
Hepatobiliary disorders	Autoimmune hepatitis	2 (0.1)	0	0
Skin and subcutaneous tissue disorders	Rash	8 (0.5)	0	0
	Pruritus	2 (0.1)	0	0

Includes legacy studies (A3671002, A3671008, A3671009, A3671022, A3671001, A3671011, A3671014, A3671015) and D4880C00003, D4880C00010, D4881C00024, D4884C00001, D4193C00003, D4190C00022 and D4191C00004. n = Number of subjects who have experienced the SAR.

^a n = number of subjects who have experienced the SAR.

^b All fatal and all life-threatening events for tremelimumab monotherapy are considered unexpected for reporting purposes.

ADR Adverse drug reaction; DCO Data cut-off; MedDRA Medical Dictionary for Regulatory Activities; PT Preferred term; RSI Reference safety information; SAR Serious adverse reaction; SOC System organ class.

A detailed summary of tremelimumab monotherapy AE data can be found in the current version of the tremelimumab IB.

1.4.2.3 Durvalumab + tremelimumab

Safety data have been pooled for 5 durvalumab and tremelimumab combination studies (D4190C00002, D4190C00006, D4190C00010, D4190C00011 and D4193C00003 [CONDOR]) for patients who received a dose of 20 mg/kg Q4W durvalumab plus 1 mg/kg tremelimumab Q4W, or equivalent durvalumab 10 mg/kg Q2W + tremelimumab 1 mg/kg Q4W; a total of 1088 patients are included in the pooled data set with a DCO of the 12 July 2017.

In durvalumab+tremelimumab combination studies at the dose of durvalumab 20 mg/kg and tremelimumab 1 mg/kg AEs (all grades) reported very commonly ($\geq 10\%$ of patients) are cough/productive cough, alteration of hepatic enzymes ALT/AST, diarrhoea, abdominal pain, hypothyroidism, rash, pruritus, pyrexia, peripheral oedema, and upper respiratory tract infections-

Approximately 15% of patients experienced an AE that resulted in permanent discontinuation of study drug and approximately 15% of patients experienced an SAE that was considered to be related to durvalumab and tremelimumab by the study investigator.

Clinical Study Protocol
Drug Substance DURVALUMAB/TREMELIMUMAB
Study Number ESR 15-11561-61-DUNE
EudraCT Nº: 2016-002858-20
Edition Number: 5.0 dated on June 09th, 2021

- Potential imAEs for durvalumab and durvalumab in combination with tremelimumab include:
 - immune-mediated pneumonitis, hepatitis, diarrhoea/colitis, intestinal perforation, hypothyroidism, adrenal insufficiency, hypophysitis/hypopituitarism, type I diabetes mellitus, nephritis, rash/dermatitis (including pemphigoid)
 - Pancreatitis
 - Other rare or less frequent events with a potential immune-mediated aetiology, eg, pericarditis, sarcoidosis, uveitis, and other events involving the eye (eg, keratitis and optic neuritis), skin (eg, scleroderma and vitiligo), and haematological (eg, haemolytic anaemia and immune thrombocytopenic purpura), rheumatological events (polymyalgia rheumatic and autoimmune arthritis) and neuropathy/neuromuscular toxicities (eg, myasthenia gravis, Guillain Barre syndrome).
- Hypersensitivity reactions including
 - Anaphylaxis and allergic reaction
 - Cytokine release syndrome
 - Immune complex disease
- Other infections

Infusion-related reactions: as with the administration of any Ig, infusion-related reactions may occur and may be severe and should be managed according to Toxicity Management Guidelines and study protocol.

Serious adverse reactions for durvalumab plus tremelimumab combination considered expected.

MedDRA (v23.0) SOC	PT	Number (%) of subjects exposed (N=2068)		
		Suspected SARs n (%) ^a	Occurrence of life-threatening suspected SARs n (%) ^b	Occurrence of fatal suspected SARs n (%) ^b
Gastrointestinal disorders	Colitis	40 (1.9)	0	0
	Diarrhoea	47 (2.3)	0	0
	Lipase increased	7 (0.3)	0	0
	Autoimmune colitis	5 (0.2)	0	0
	Abdominal pain	4 (0.2)	0	0
	Enterocolitis	6 (0.3)	0	0
Respiratory, thoracic, and mediastinal disorders	Amylase increased	3 (0.1)	0	0
	Pneumonitis	29 (1.4)	0	0
	Interstitial lung disease	9 (0.4)	0	0
Endocrine disorders	Adrenal insufficiency	14 (0.7)	0	0
	Hyperthyroidism	4 (0.2)	0	0
	Hypopituitarism	5 (0.2)	0	0
	Hypophysitis	4 (0.2)	0	0
General disorders and administration site conditions	Pyrexia	7 (0.3)	0	0
	Oedema peripheral	2 (<0.1)	0	0
Hepatobiliary disorders	Autoimmune hepatitis	5 (0.2)	0	0
	Hepatitis	4 (0.2)	0	0
Infections and infestations	Pneumonia	9 (0.4)	0	0
Cardiac disorders	Myocarditis	2 (<0.1)	0	0
Injury, poisoning, and procedural complications	Infusion related reaction	3 (0.1)	0	0
Renal and Urinary disorders	Nephritis	2 (<0.1)	0	0
Skin and subcutaneous tissue disorders	Pemphigoid	2 (<0.1)	0	0

Investigations	AST increased	5 (0.2)	0	0
	ALT increased	2 (<0.1)	0	0
	Transaminases increased	2 (<0.1)	0	0

Pooled dataset from studies D4190C00002, D4190C00006, D4190C00010, D4190C00011, D4190C00021, D4190C00022, ARCTIC, EAGLE, MYSTIC, and CONDOR.

^a n = number of subjects who have experienced the SAR.

^b All fatal and all life-threatening events for durvalumab + tremelimumab are considered unexpected for reporting purposes and are excluded from this table.

ALT = alanine aminotransferase; AST = aspartate aminotransferase; DCO = data cut-off; MedDRA = Medical Dictionary for Regulatory Activities;

PT = preferred term; SAR = serious adverse reaction; SOC = system organ class.

A detailed summary of durvalumab + tremelimumab combination AE data can be found in the current version of the durvalumab IB.

1.4.2.4 Fixed Dosing for durvalumab and tremelimumab

A population PK model was developed for durvalumab using monotherapy data from a Phase 1 study (study 1108; N=292; doses= 0.1 to 10 mg/kg Q2W or 15 mg/kg Q3W; solid tumors). Population PK analysis indicated only minor impact of body weight (WT) on PK of durvalumab (coefficient of ≤ 0.5). The impact of body WT-based (10 mg/kg Q2W) and fixed dosing (750 mg Q2W) of durvalumab was evaluated by comparing predicted steady state PK concentrations (5th, median and 95th percentiles) using the population PK model. A fixed dose of 750 mg was selected to approximate 10 mg/kg (based on median body WT of ~75 kg). A total of 1000 patients were simulated using body WT distribution of 40–120 kg. Simulation results demonstrate that body

Clinical Study Protocol
 Drug Substance DURVALUMAB/TREMELIMUMAB
 Study Number ESR 15-11561-61-DUNE
 EudraCT Nº: 2016-002858-20
 Edition Number: 5.0 dated on June 09th, 2021

WT-based and fixed dosing regimens yield similar median steady state PK concentrations with slightly less overall between-subject variability with fixed dosing regimen.

Similarly, a population PK model was developed for tremelimumab using data from Phase 1 through Phase 3 ($N=654$; doses= 0.01 to 15 mg/kg Q4W or Q90D; *metastatic melanoma*) [Wang et al. 2014]. Population PK model indicated minor impact of body WT on PK of tremelimumab (coefficient of ≤ 0.5). The WT-based (1 mg/kg Q4W) and fixed dosing (75 mg/kg Q4W; based on median body WT of ~ 75 kg) regimens were compared using predicted PK concentrations (5th, median and 95th percentiles) using population PK model in a simulated population of 1000 patients with body weight distribution of 40 to 120 kg. Similar to durvalumab, simulations indicated that both body WT-based and fixed dosing regimens of tremelimumab yield similar median steady state PK concentrations with slightly less between-subject variability with fixed dosing regimen.

Similar findings have been reported by others [Ng et al 2006, Wang et al 2009, Zhang et al 2012, Narwal et al 2013]. Wang and colleagues investigated 12 monoclonal antibodies and found that fixed and body size-based dosing perform similarly, with fixed dosing being better for 7 of 12 antibodies. In addition, they investigated 18 therapeutic proteins and peptides and showed that fixed dosing performed better for 12 of 18 in terms of reducing the between-subject variability in pharmacokinetic/pharmacodynamics parameters [Zhang et al 2012].

A fixed dosing approach is preferred by the prescribing community due to ease of use and reduced dosing errors. Given expectation of similar pharmacokinetic exposure and variability, we considered it feasible to switch to fixed dosing regimens. Based on average body WT of 75 kg, a fixed dose of 750 mg Q2W MEDI4736 (equivalent to 10 mg/kg Q2W), 1500 mg Q4W durvalumab (equivalent to 20 mg/kg Q4W) and 75 mg Q4W tremelimumab (equivalent to 1 mg/kg Q4W) is included in the current study.

Fixed dosing of durvalumab and tremelimumab is recommended only for subjects with more or equal than 30kg body weight due to endotoxin exposure. Patients with a body weight less than 30 kg should be dosed using a weight-based dosing schedule.

2. STUDY OBJECTIVES

2.1 Primary objective(s)

The study will include patients with advanced neuroendocrine neoplasms in four different cohorts with the following primary endpoints:

Primary endpoint for cohorts 1, 2 and 3:

Nine-months clinical benefit rate (CBR) by Response Evaluation Criteria In Solid Tumors (RECIST 1.1), which is defined as the percentage of patients achieving complete response (CR), partial response (PR), or stable disease (SD) at month 9 after durvalumab plus tremelimumab was started.

Primary endpoint for cohort 4:

Nine-months overall survival rate, which is defined as the percentage of patients alive at month 9 after durvalumab plus tremelimumab was started.

Clinical Study Protocol
 Drug Substance DURVALUMAB/TREMELIMUMAB
 Study Number ESR 15-11561-61-DUNE
 EudraCT Nº: 2016-002858-20
 Edition Number: 5.0 dated on June 09th, 2021

2.2 Secondary objective(s)

- Overall response rate (ORR) by irRECIST.
- To assess the duration of response according to irRECIST.
- To assess the median progression-free survival time (PFS) according to irRECIST.
- To assess the safety profile of Durvalumab and Tremelimumab in subjects with advanced neuroendocrine neoplasms.
- To assess the median overall survival (OS) time.
- To assess response status according to irRECIST at 6 and 12 months after start of study treatment.

2.3 Exploratory objective(s)

- To evaluate biochemical response (changes in CgA and NSE levels) and its association with response rate and progression-free survival.
- To assess whether baseline tumor and blood biomarkers may be predictive of response to durvalumab and tremelimumab therapy.
- To explore additional hypotheses related to biomarkers and relationship to durvalumab and tremelimumab efficacy and/or toxicity and neuroendocrine tumors evolution that may arise from internal or external research activities.

3. STUDY DESIGN

3.1 Overview of study design

This is a prospective, multi-center, open label, stratified, exploratory phase II study evaluating the efficacy and safety of durvalumab plus tremelimumab in different cohorts of patients with neuroendocrine neoplasms.

The study will include patients in four different cohorts:

- **Cohort 1:** Well-moderately differentiated lung neuroendocrine tumors (classically known as typical and atypical carcinoids) after progression to somatostatin analogs and one prior targeted therapy or chemotherapy.
- **Cohort 2:** G1/G2 (WHO grade 1 and 2) gastrointestinal neuroendocrine tumors after progression to somatostatin analogs and one prior targeted therapy.
- **Cohort 3:** G1/G2 (WHO grade 1 and 2) pancreatic neuroendocrine tumors after progression to standard therapies (chemotherapy, somatostatin analogs and target therapy), who have received between two and four prior lines of treatment.

Clinical Study Protocol
 Drug Substance DURVALUMAB/TREMELIMUMAB
 Study Number ESR 15-11561-61-DUNE
 EudraCT Nº: 2016-002858-20
 Edition Number: 5.0 dated on June 09th, 2021

- **Cohort 4:** Neuroendocrine neoplasms (WHO grade 3) of gastroenteropancreatic origin or unknown primary site (excluding lung primary tumors), patients will be treated in second line only, after progression to first-line chemotherapy with a platinum based regimen.

The patient recruitment period of the study will last approximately 24 months. The maximum treatment period for each subject on study is anticipated to be approximately 12 months (13 administrations of durvalumab). However, subjects will continue on active follow-up to determine secondary endpoints of duration of response, median progression-free survival, median overall survival and safety profile.

This study will be conducted in 3 phases: a screening phase, a treatment phase stratified by tumor origin (four different cohort) and a follow up phase.

3.2 Study schema

Screening phase

Screening will occur between Day -28 and Day -1. The purpose of the screening period is to establish protocol eligibility. Informed consent will be obtained up to 4 weeks prior to Cycle 1 Day 1 and after the study has been fully explained to each subject and prior to the conduct of any screening procedures or assessments.

The purpose of the baseline visit is to establish disease characteristics prior to allocation and treatment and to confirm protocol eligibility as specified in the inclusion/exclusion criteria. Results of baseline assessments must be obtained prior to the first dose of study drug (Cycle 1/Day 1). Baseline assessments may be performed on Day -1 or on Cycle 1/Day 1 prior to dosing. Clinical laboratory tests including pregnancy test (where applicable) can be performed within 72 hours of the first dose of study drug. Subjects who complete the baseline visit and continue to meet the criteria for inclusion/exclusion will begin the treatment phase of this study.

Determinations performed by routine clinical practice before signing the informed consent will be valid, provided they are carried out following this protocol requirements and date of baseline TC is performed within the previous 4 weeks from treatment initiation. It should be clearly stated that patient consented her/his participation to ESR 15-11561-61-DUNE trial in patient record.

Treatment phase

The treatment phase will begin at the time of allocation of the first patient and will consist of the study treatment cycles. The treatment phase will end when the last patient discontinue the study drug.

The treatment phase will include two stages for each cohort. The first stage will dose the first patient in each cohort in a safety run period for one cycle (4 weeks). If no unexpected side effects are observed in the first patient treated in each cohort during the safety run period, recruitment will continue up to 31 patients for cohorts 1 to 3, and 33 for cohort 4.

Subjects will be allocated in each primary tumor cohort to receive durvalumab 1500 mg Q4W for 12 months plus tremelimumab 75 mg Q4W for up to 4 doses during the first 4 cycles of combined therapy. Cycles are defined by 4 weeks or 28 days. Subjects will undergo safety and efficacy assessment as defined per protocol.

If a toxicities pause occurs, cycles not administered for that toxicity can be delayed for a maximum of 4 weeks, after that time that cycle will be considered lost and the next cycle will be administered.

Clinical Study Protocol
Drug Substance DURVALUMAB/TREMELIMUMAB
Study Number ESR 15-11561-61-DUNE
EudraCT N°: 2016-002858-20
Edition Number: 5.0 dated on June 09th, 2021

Remember no restarts are allowed after a delay of more than 12 weeks due to toxicity or more than 4 weeks of delay if the **reason is different from toxicity** without consulting the Coordinating Investigator.

Follow-up phase

Patients will finish the treatment phase after the administration of 12 months (13 cycles) of durvalumab or after disease progression during the treatment phase. For patients that complete all scheduled treatment, the follow-up phase will begin to determine survival endpoints. Tumor assessments will continue every 12 weeks and clinical appointments will start monthly during the first 3 months of follow-up, every 2 months until first year, and continue every 6 months until disease progression.

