5.2 Dose and treatment regimens

5.2.1 Treatment regimen

Patients will receive 1500 mg durvalumab via IV infusion q4w for up to 4 doses/cycles and 75 mg tremelimumab via IV infusion q4w for up to 4 doses/cycles, and then continue 1500 mg durvalumab q4w starting on Week 16 for up to 8 months (9 doses). Dosing outside the window should be discussed with the Study Physician. Tremelimumab will be administered first. Durvalumab infusion will start approximately 1 hour after the end of tremelimumab infusion. The duration will be approximately 1 hour for each infusion. A 1-hour observation period is required after the first infusion of durvalumab and tremelimumab. If no clinically significant infusion reactions are observed during or after the first cycle, subsequent infusion observation periods can be at the Investigator's discretion (suggested 30 minutes after each durvalumab and tremelimumab infusion).

Clinical Study Protocol
 Drug Substance DURVALUMAB/TREMELIMUMAB
 Study Number ESR 15-11561-61-DUNE
 EudraCT Nº: 2016-002858-20
 Edition Number: 5.0 dated on June 09th, 2021

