Clinical Study Protocol
Drug Substance DURVALUMAB/TREMELIMUMAB
Study Number ESR 15-11561-61-DUNE
EudraCT Nº: 2016-002858-20
Edition Number: 5.0 dated on June 09th, 2021

- Urinalysis (see Table 6)
- Administer study drug.
- Collect blood samples for biomarker analysis.
- Record all concomitant medication use.
- Record any AEs or SAEs.
- Record survival data.

Cycle 2/Day 15

- Evaluate ECOG performance status.
- Obtain vital signs (supine BP, HR, RR, body temperature) and weight.
- Perform a comprehensive physical examination (including a neurological evaluation). A symptom-directed physical examination will be performed at any time during the study, as clinically indicated.
- Collect blood samples for biochemistry and hematology analyses (see Tables 4 and 5), including TSH, fT3 and fT4.
- Urinalysis (see Table 6)
- Record all concomitant medication use.
- Record any AEs or SAEs.

Cycle 3/Day 1

- Evaluate ECOG performance status.
- Obtain vital signs (supine BP, HR, RR, body temperature) and weight.
- Perform a comprehensive physical examination (including a neurological evaluation). A symptom-directed physical examination will be performed at any time during the study, as clinically indicated.
- Collect blood samples for biochemistry and hematology analyses (see Tables 4 and 5), including TSH, fT3 and fT4.
- Urinalysis (see Table 6)
- Administer study drugs.
- Record all concomitant medication use.
- Record any AEs or SAEs.
- Record Survival data

Cycle 3/Day 15

- Evaluate ECOG performance status.

- Obtain vital signs (supine BP, HR, RR, body temperature) and weight.
- Perform a comprehensive physical examination (including a neurological evaluation). A symptom-directed physical examination will be performed at any time during the study, as clinically indicated.
- Collect blood samples for biochemistry and hematology analyses (see Tables 4 and 5), including TSH, fT3 and fT4.
- Urinalysis (see Table 6)
- Record all concomitant medication use.
- Record any AEs or SAEs.

Cycle 4 Through Last Cycle (cycle 12)/Day 1

- Evaluate ECOG performance status.
- Obtain vital signs (supine BP, HR, RR, body temperature) and weight.
- Perform a comprehensive physical examination (including a neurological evaluation). A symptom-directed physical examination will be performed at any time during the study, as clinically indicated.
- Collect blood samples for biochemistry and hematology analyses (see Tables 4 and 5), including TSH, fT3 and fT4
- Urinalysis (see Table 6)

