Patients will finish the treatment phase after the administration of 12 cycles of durvalumab or after disease progression during the treatment phase. For patients that complete all scheduled treatment, the follow-up phase will begin to determine survival endpoints. Tumor assessments will continue every 12 weeks and clinical appointments will start monthly during the first 3 months of follow-up and continue every 12 weeks until disease progression.

End of Treatment

End of treatment is defined as the last planned dosing visit within the 12-month dosing period. For subjects who discontinue durvalumab or tremelimumab prior to 12 months, end of treatment is considered the last visit where the decision is made to discontinue treatment. All required procedures may be completed within \pm 7 days of the end of treatment visit. Repeat disease assessment is not required if performed within 28 days prior to the end of treatment visit. Blood samples for biomarker analysis are collected. Assessments for subjects who have completed durvalumab and tremelimumab treatment and achieved disease control, or have discontinued durvalumab or tremelimumab due to toxicity in the absence of confirmed progressive disease are provided in APPENDIX 2 of the protocol.

Assessments for subjects who have discontinued durvalumab or tremelimumab treatment due to confirmed PD are presented in APPENDIX 3 of the protocol.

All subjects will be followed for survival until the end of the study regardless of further treatments,

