1.3 STUDY MEDICATION

For the descriptive analysis of the patients, the full analysis set is used (see section 29).

Table 82 Adherence to Durvalumab

	n	Mean (SD)	Median (IQR)	Min-Max	95% CI of the mean
Cycles received					
12 Cycles received	n		% ¹		95% CI of the proportion
Yes					
No					
Cycles received	n		% ¹		95% CI of the proportion
0					
1					
2					
3					
4					
5					
6					
7					
8					

9				
10				
11				
12				
Cycles delayed	n	%¹	95% CI of the proportion	
Yes				
No				
	n	Mean (SD)	Median (IQR)	Min-Max
Cycles delayed				
Cycles omitted	n	%¹	95% CI of the proportion	
Yes				
No				
	n	Mean (SD)	Median (IQR)	Min-Max
Cycles omitted				
¹ Calculated percentage from the total of patients with available data				
Table 83 Adherence to Tremelimumab				
Cycles received	n	Mean (SD)	Median (IQR)	Min-Max
4 Cycles received	n	%¹	95% CI of the proportion	
Yes				
No				
Cycles received	n	%¹	95% CI of the proportion	
0				
1				
2				
3				
4				
Cycles delayed	n	%¹	95% CI of the proportion	
Yes				
No				
	n	Mean (SD)	Median (IQR)	Min-Max
Cycles delayed				
Cycles omitted	n	%¹	95% CI of the proportion	
Yes				
No				

	n	Mean (SD)	Median (IQR)	Min-Max	95% CI of the mean
--	----------	------------------	---------------------	----------------	---------------------------

Cycles omitted

¹ Calculated percentage from the total of patients with available data

1.3.1 Study medication in cohort 1

For the descriptive analysis of the patients, the full analysis set is used (see section 29).

Table 84 Adherence to Durvalumab in cohort 1

	n	Mean (SD)	Median (IQR)	Min-Max	95% CI of the mean
Cycles received					
12 Cycles received	n		%¹		95% CI of the proportion
Yes					
No					
Cycles received	n		%¹		95% CI of the proportion
0					
1					
2					
3					
4					
5					
6					
7					
8					
9					
10					
11					
12					
Cycles delayed	n		%¹		95% CI of the proportion
Yes					
No					
	n	Mean (SD)	Median (IQR)	Min-Max	95% CI of the mean
Cycles delayed					
Cycles omitted	n		%¹		95% CI of the proportion
Yes					
No					

	n	Mean (SD)	Median (IQR)	Min-Max	95% CI of the mean
--	---	-----------	--------------	---------	--------------------

Cycles omitted

¹ Calculated percentage from the total of patients with available data

Table 85 Adherence to Tremelimumab in cohort 1

	n	Mean (SD)	Median (IQR)	Min-Max	95% CI of the mean
Cycles received					
4 Cycles received	n		% ¹		95% CI of the proportion
Yes					
No					
Cycles received	n		% ¹		95% CI of the proportion

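### The protocol plans 13 durvalumab doses in its design and regimen sections but 12 in its visit schedule and section 8.1.2; the SAP uses 12, so its completion category does not fit the 13-dose reading

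*Protocol*

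**What the plan says.** **Thirteen doses, in the protocol:**
- Section 3.1 puts the maximum treatment period at "approximately 12 months (13 administrations of durvalumab".
- Section 3.2 (follow-up phase) ends treatment "after the administration of 12 months (13 cycles) of durvalumab".
- Section 5.2.1 gives "1500 mg durvalumab via IV infusion q4w for up to 4 doses/cycles" with tremelimumab, then durvalumab alone "starting on Week 16 for up to 8 months (9 doses".
- Section 5.2.2 repeats the 4 + 9 pattern for retreatment.

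**Twelve doses, in the same protocol:**
- Section 8.1.2 heads its last block of visits "Cycle 4 Through Last Cycle (cycle 12)/Day 1" and has durvalumab given alone from C5D1 to C12D1.
- The schedule of study assessments has C12D1 as its last dosing visit.

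**Twelve doses, in the SAP:**
- Section 3.4 ends the treatment phase "after the administration of 12 cycles of durvalumab".
- Section 3.5 and Table 1 run to cycle 12.
- Tables 82, 84, 86, 88 and 90 (section 1.3, Study medication) contain a yes/no item "12 Cycles received" and count rows from 0 to 12. They also have a numeric summary of cycles received and items for delayed and omitted cycles.

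SAP section 5.3 says the SAP was written for protocol version 3.1 of November 2017.

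**The concern.** The planned number of doses sets several later definitions. Section 8.1.3 defines end of treatment, for patients who are not stopped early, as the last planned dosing visit in the 12-month period, and the end-of-treatment biomarker sample belongs to that visit. The 90-day adverse event window (section 10.3.1) and the follow-up visits (Appendix 2) run from the last dose. With two planned numbers, all of these can move by one cycle, and two sites reading different sections could act differently.

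The SAP tables carry the conflict into reporting. They fix completion at 12 cycles, while four protocol sections describe a 13-dose course. The omitted-cycles item also needs a planned number as its reference. Section 3.2 treats a cycle delayed beyond 4 weeks as lost. A patient who stops after 12 doses therefore has 0 or 1 omitted cycles, depending on the section read.

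**Working it through.** This is a count of doses at 4-week spacing; no sample-size figure is involved. Section 3.2 sets the spacing: "Cycles are defined by 4 weeks or 28 days". Dose *n* falls at week 4(*n* − 1), on day 28(*n* − 1) + 1. Cycle *n* ends at 28*n* days. Months use 30.4375 days.

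**Step 1, the protocol's figure of 13.** Section 5.2.1 gives 4 combination doses at weeks 0, 4, 8 and 12. It then gives 9 doses from week 16, the last at week 16 + 4 × 8 = 48. The total is 4 + 9 = 13, which agrees with sections 3.1 and 3.2.

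**Step 2, section 8.1.2 and the visit schedule.** C1 to C12 is 12 doses. C5 to C12 is 8 durvalumab-only doses, against 9 in section 5.2.1.

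**Step 3, side by side.**

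| | 12 doses | 13 doses |
|---|---|---|
| Durvalumab-only doses | 8 | 9 |
| Last dose | week 44, day 309 | week 48, day 337 |
| End of last cycle | 336 days, 11.04 months | 364 days, 11.96 months |
| Cumulative at 1500 mg per dose | 18,000 mg | 19,500 mg |

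The difference is one dose, 4 weeks and 1,500 mg, or 1/13 = 7.7% of the 13-dose course. The 12-month limit does not decide between the two, because days 309 and 337 both lie inside it.

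**Step 4, the SAP tables under the 13-dose reading.**
- Counts of 0 to 11 are placed correctly.
- A count of 12 is scored as complete although one planned dose is missing.
- A count of 13 has no row.
- The numeric summary (n, mean, median, range) can hold 13 without change.

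Under the 12-dose reading the tables are correct for the initial course.

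**Step 5, the primary endpoints.** Month 9 is 9 × 30.4375 = 273.9 days, about week 39. Doses 12 and 13, at weeks 44 and 48, come later for anyone dosed without delay.

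**Step 6, who is affected.** Only patients still on durvalumab at about weeks 44 to 48. The documents do not give that number. As a rough guide, section 11.3 assumes 30% to 50% progression-free at 9 months in cohorts 1 to 3 (93 patients) and 13% to 23% alive at 9 months in cohort 4 (33 patients). That is 27.9 to 46.5 plus 4.3 to 7.6, or about 32 to 54 of 126. These are month-9 figures, and treatment past progression is allowed, so they are only an indication.

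**The case against.** The strongest reply is that little depends on this. Adherence is not a primary, secondary or exploratory objective, the tables are descriptive, and the SAP agrees with itself. Section 3.1 calls the duration approximate and section 5.2.1 states maxima, so actual doses will vary anyway. By the section 13.6 timetable the last patient entered in December 2019, about 18 months before Edition 5.0 (June 2021). Most first-course dosing should then have been over. All of this stands, and it limits the weight of the point. It does not remove the conflict: a maximum still has to be one number, and the SAP's older base version cannot explain a contradiction inside Edition 5.0.

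A reader might infer more than the documents support:
- *That adherence cannot be tabulated at all.* Only the top category, the completion item and possibly omitted cycles are at issue.
- *That sites did stop at different points.* Nothing shows this; it is a possibility that the text leaves open.
- *That every patient who reaches end of treatment is affected.* Section 8.1.3 applies that term to early discontinuers too, and their end of treatment is clear.
- *That tumour assessment shifts.* Appendix 2 times scans from the first infusion.
- *That the visit numbering settles the matter.* The header pairs V10–V16 (7 visits) with C5–C12 (8 cycles). That table may have been damaged in text extraction; section 8.1.2 carries the point without it.

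**Conclusion.** The inconsistency is real and unreconciled: 13 doses in four protocol sections, 12 in section 8.1.2 and the visit schedule, and 12 throughout the SAP. Its size is one dose, or 4 weeks, for patients who stay on treatment to the end of the 12-month period. If 13 is the intended number, the five durvalumab tables misclassify 12-dose and 13-dose patients and may undercount omitted cycles by one. If 12 is intended, the tables stand and the other protocol sections are wrong. The documents do not settle which, and this review does not either.

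The 9-month primary endpoints are essentially unaffected, assuming doses are given without delay. The point should be corrected before the exposure and adherence results are reported, but it does not threaten the main efficacy conclusions.

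**What to change.** 1. The sponsor reconciles protocol sections 3.1, 3.2, 5.2.1, 5.2.2 and 8.1.2 and the schedule of assessments, with SAP sections 3.4 and 3.5 and Table 1, to one number of durvalumab doses.
2. SAP Tables 82, 84, 86, 88 and 90 use that number as the top category, as the definition of completion and as the reference for omitted cycles, for the initial course only.
3. Retreatment doses are tabulated separately. Section 5.2.2 allows a further 4 + 9, which no single top category for the initial course would hold.

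The cost is protocol and SAP wording and five table shells. No new data are needed if actual doses are recorded. Section 13.6 dates the clinical study report December 2022, after Edition 5.0, so on that timetable the tables could still be corrected.
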